To calculate number of subjects needed per group and provide 80% power at $\alpha=0.05$ we used mean differences and standard deviation (EMIQ: 19 ± 24.62 and Placebo: 1 ± 12.87) of whole abdominal fat loss from an early published study conducted in Japan, where the Japanese volunteers consumed 275mg EMIQ per day for 12 weeks and showed a positive impact of EMIQ on reduction of fat depots. We plugged in data from that study into this formula $N=1+[16(xS^2/d^2)]$ to calculate sample size. Using this formula the number of subjects in each group were calculated to be $n=18$. However, we selected to use 25 subjects per group which increases power of study to $>85\%$. 25 subjects per group is a conservative sample size, which make us to expect a larger difference in the means with a higher dose of EMIQ intake.

The primary objective of this study is to demonstrate reduction of total body fat following 12 weeks of EMIQ intervention. Therefore, we will determine statistically if EMIQ is effective to reduce percent body weight, total abdominal fat, subcutaneous and visceral fat after 12 weeks of intervention compared to baseline values. We plan to compare the two group medians with the Mann-Whitney U test. After reviewing the data at the completion of the study, we can assume normality, then we will compare the two group means with parametric t-test.

C. Subject Characteristics

Inclusion Criteria:

- Male or female age 18-65 years.
- Premenopausal female with regular menstrual cycle or post-menopausal female with cessation of menstrual cycle for a minimum of 6 months.
- BMI in the range of 26.0-37.0_
- Beck Depression Inventory Score less than 20.
- Fluency in spoken or written English.
- Willingness to be randomized to take EMIQ or placebo.
- Must weigh at least 164lbs

Exclusion Criteria:

- Any major illness or condition that may interfere with study outcomes at the discretion of the study physician.
- Diabetes Type I & Type II, or use of any pharmacological treatment for diabetes.
- Use of medications that interfere with energy metabolism
- Receiving hormone therapy growth hormone, testosterone, or estrogen with the exception of hormone contraceptives.
- GI diseases, conditions or medications known to influence GI absorption including active peptic ulcer disease or inflammatory bowel disease such as

- ulcerative colitis, Crohn's disease, celiac disease, chronic diarrhea or constipation.
- Undergone gastric bypass or other bariatric weight loss procedure.

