In order to monitor adherence and safety of EMIQ intake over the 12 week of the study, volunteers will undergo electrocardiogram (EKG) testing as well as several hematological tests, liver functions tests and other biochemical tests (See below) carried out on the collected blood samples. In addition, volunteers will be asked to provide a spot urine sample during screening and visits 2 and 5 to measure total protein, glucose, urobilinogen, bilirubin, ketones, pH and occult blood in urine using urine dip stick test. Volunteers will complete three (3) 24-hour dietary recalls over the phone at three time points: between visit 1 and visit 2; between visit 3 and visit 4 (around week 6 from beginning the supplement); and between visit 4 and visit 5 (around weeks 11-12) to estimate total caloric intake and intake of three major nutrient groups: protein, carbohydrates, and fat. Volunteers will be asked to bring back unused EMIQ capsules and a compliance calendar during each visit to determine adherence to the supplementation schedule. Volunteers will be asked not to change their regular physical activity, and will fill out a 7-day physical activity record at visits 2, 3, 4 and 5 to monitor this. To assess changes in adiposity following EMIQ intervention, the volunteers will complete whole body and segmental Dual X-ray Absorptiometry (DXA), skinfold thickness and hip to waist circumferences measurements at visit 2, i.e., before the intervention, and after 12 weeks of intervention, at visit 5, for total and segmental changes in body fat and fat free

mass. DXA data will be further subjected to computational analysis to obtain changes in abdominal, visceral and subcutaneous fats.

Per policy number 9.20.18.30 of Tufts Department of Pharmacy Policy and Procedure Manual, any supplement returned from study subjects, or leftover upon completion of the study, will be destroyed “on-site” by placing them in a chemotherapy waste container for disposal using the Hospital’s system.

The following is a summary of the 6 total visits required by volunteers in this study:

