## Statistical Analysis Plan

All subjects who completed the study were included in the analysis. Summary statistics were expressed in mean  $\pm$  S.D. for continuous variables, and counts (percentage %) for categorical variables. Differences between treatment groups were tested using Student's *t*-test. Two-sample Wilcoxon test is used when variables appear to violate distributional assumptions. Model assumptions were assessed within an ANCOVA model predicting 12 week outcome, adjusting for baseline. Fisher's exact test or chi-square test was performed for categorical variables. An  $\alpha$  level of  $p < 0.05$  was considered statistically significant. Statistical analysis was conducted in R 3.4 (R Core Team 2017, Vienna Austria).

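### As worded, the SAP uses its baseline-adjusted ANCOVA only to check assumptions and tests treatment with an unadjusted test on an unstated scale; making the ANCOVA the comparison is a modest, cheap improvement

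*SAP*

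**What the plan says.** **SAP, Statistical Analysis Plan.** The default comparison is "Differences between treatment groups were tested using" Student's t-test. The fallback is: "Two-sample Wilcoxon test is used when variables appear to violate distributional assumptions". ANCOVA appears once: "Model assumptions were assessed within an ANCOVA model predicting 12 week outcome, adjusting for baseline". No sentence says that the treatment effect is estimated or tested from that model. The SAP does not say whether the tests use the week-12 value, the change or the percent change, and it gives no diagnostic or threshold for moving from one test to the other.

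**Protocol III.B, Sample Size and Statistical Analyses.** "The primary objective of this study is to demonstrate reduction of total body fat following 12 weeks of EMIQ intervention". The test is stated as: "We plan to compare the two group medians with the Mann-Whitney U test". The t-test comes second: "After reviewing the data at the completion of the study, we can assume normality, then we will compare the two group means". ANCOVA is not mentioned.

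**Scale in the protocol.** III.B speaks of the fat measures "after 12 weeks of intervention compared to baseline values". III.E.I (Overview) introduces the body-composition measurements with "To assess changes in adiposity following EMIQ intervention". III.H (Outcome) predicts a between-group difference in the change in total body fat. The sample size in III.B is also built on fat loss. So the protocol points to change, but never ties that scale to the test.

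**Data.** III.E.IV (Study Assessments) schedules DXA at visits 2 and 5, so each completer should have a baseline and a week-12 value.

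**The concern.** Three things are left loose.

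1. **Model mismatch.** Residuals of a week-12 ANCOVA with baseline as covariate are not the quantities whose distribution matters for an unadjusted two-sample t-test. Either the check belongs to a different analysis from the one reported, or ANCOVA was the intended analysis and the SAP does not say so.
2. **Scale.** A reader of the SAP cannot tell which variable enters the test. ANCOVA would settle this: with baseline as covariate, modelling the week-12 value or the change gives the same treatment difference, because subtracting baseline from the outcome only lowers the baseline slope by one.
3. **Choice of test.** In both documents the choice follows inspection of the data, with no objective rule.

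At stake are some precision, protection of the estimate against a chance baseline difference, and a primary result that is fixed in advance. The validity of the randomised comparison is not at stake.

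**Working it through.** **Inputs from protocol III.B.** Whole abdominal fat loss 19 (SD 24.62) on EMIQ and 1 (SD 12.87) on placebo, so the difference is d = 18; 25 per group; alpha 0.05, taken as two-sided because the constant 16 in the formula implies it. These figures stand in for total body fat. **Assumed, not in the documents:** the correlation r between baseline and week 12, shown at 0.8, 0.9 and 0.95, with equal SDs at the two times.

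**The plan's own figure.** N = 1 + 16·S²/d². With the mean of the two SDs, S = (24.62 + 12.87)/2 = 18.745, N = 1 + 16 × 351.4/324 = 18.35, matching the stated 18. With the root-mean-square SD, S = √((24.62² + 12.87²)/2) = 19.64, N = 20.06. Noncentral-t power at 25 per group is 91.4% and 88.8% respectively, so the stated power above 85% holds for an unadjusted t-test on change. The working below uses 19.64 as the SD of change.

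**SDs on each scale**
- Week-12 value: SD_F = 19.64/√(2(1 − r))
- ANCOVA residual: SD_A = SD_F × √(1 − r²)

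| r | SD_F | SD_A | Power, t on change | Power, ANCOVA (47 df) |
|---|---|---|---|---|
| 0.80 | 31.06 | 18.64 | 88.8% | 91.7% |
| 0.90 | 43.93 | 19.15 | 88.8% | 90.2% |
| 0.95 | 62.12 | 19.40 | 88.8% | 89.5% |

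The formula does not charge ANCOVA for estimating the baseline slope. Simulation does (bivariate normal, 100,000 runs per cell). With equal arm SDs, ANCOVA against t on change gives 91.0 v 88.7%, 89.6 v 88.8% and 88.7 v 88.7%. With the planning SDs by arm it gives 91.1 v 88.7%, 89.5 v 88.6% and 88.6 v 88.5%. The gain is about 2.4, 0.8 and 0 points. At r = 0.98 the sign turns: ANCOVA is about 0.4 of a point lower. Type I error at the planning SDs with 25 per group is about 5.2% for both tests.

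**Chance baseline imbalance.** The chance of a difference above 0.3 SD in either direction is 2(1 − Φ(0.3/√(2/25))) = 2(1 − Φ(1.061)) = 0.289. It moves the expected change-score difference by (1 − r) × 0.3 × SD_F:
- r = 0.80: 0.20 × 0.3 × 31.06 = 1.86, or 10% of 18
- r = 0.90: 0.10 × 0.3 × 43.93 = 1.32, or 7%
- r = 0.95: 0.05 × 0.3 × 62.12 = 0.93, or 5%

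ANCOVA removes this shift.

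**Non-normal errors.** With d and the change SD unchanged, a normal baseline and illustrative error shapes that are not in the documents (60,000 runs per cell):

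| Errors | r | ANCOVA | Rank test on change |
|---|---|---|---|
| t, 3 df | 0.80 / 0.90 / 0.95 | 91.7 / 90.4 / 90.2% | 97.3 / 97.7 / 97.9% |
| Lognormal, log-SD 0.8 | 0.80 / 0.90 / 0.95 | 89.8 / 89.0 / 88.4% | 98.7 / 99.2 / 99.2% |

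Here ANCOVA gives up roughly 5 to 11 points to the rank test.

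**The case against.** **The reversed order is mostly cosmetic.** This stands. Both documents lead to the t-test when normality is accepted and to the rank test when it is not. A reader might infer that protocol and SAP prescribe conflicting analyses. They differ only when the normality judgement is borderline.

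**The gain is small, and the rank test can be better.** This also stands. A 0.3 SD imbalance can fall either way, so it is noise and not bias. Where the rank fallback would actually operate, replacing it with ANCOVA can cost more power than ANCOVA gains under normality. That is why the rank test should always be reported and not deleted.

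**The ANCOVA sentence may be loose drafting for the analysis model.** Possible. In that case the repair is one sentence, but it is still needed, because as written the sentence assigns the model only to checking assumptions.

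**Power could collapse if raw week-12 values were tested.** A reader might infer this from the SAP's silence on scale together with its week-12 model. On the same inputs, power would be 81%, 69% and 52% at r = 0.6, 0.7 and 0.8. The documents do not support taking this as the plan: the protocol's statistics, overview and outcome sections, and the basis of its sample size, all point to change. It is a reason to state the scale, not a measure of the defect.

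**It may be too late.** The SAP is largely in the past tense, so an edit may not restore pre-specification. That limits the remedy to disclosure and an added estimate if the analysis has been run.

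**Conclusion.** The point holds as one of specification with a modest statistical benefit. As worded, the SAP's adjusted model does not produce the treatment comparison, and its assumption check belongs to a different model from the test reported. The test's scale and the trigger for switching are also not fixed.

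A reader might go further and call the unadjusted analysis invalid or biased. It is neither: randomisation supports it, and the planned power is reproduced for a t-test on change. The case for ANCOVA is that it settles the scale, uses data already scheduled, matches a model the SAP already describes and removes chance imbalance.

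The power and imbalance figures rest on the planning SDs for abdominal fat and on correlations that the documents do not give. The power gain also assumes roughly normal errors. The wording findings rest on none of these assumptions. This should be corrected, but it is not a threat to the trial's conclusions.

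**What to change.** In both documents:

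- State that the treatment comparison is an ANCOVA of 12-week total body fat on treatment group with baseline as covariate. Use the same model for the other fat measures.
- Report the adjusted difference with its 95% CI, whatever the distributional check shows.
- Replace the data-dependent switch with a stated sensitivity analysis that is always reported: the rank test on change from baseline.

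If the analysis has already been run, report the ANCOVA estimate beside it and disclose which test and scale were used. Do not describe the ANCOVA as pre-specified.

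**Cost.** One paragraph in each document and no new data. Statistically, ANCOVA spends one residual degree of freedom, which costs a fraction of a power point at correlations near 0.98 or above. The larger possible cost is the loss against the rank test when errors are clearly heavy-tailed or skewed; showing the rank result every time keeps that information in view.

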Version Date: 3/2/2018

Principal Investigator: [name]

Co-Investigator: [name]

Study Physician: [name]

Study Title: Body Fat Reducing Effect and Safety of Enzymatically Modified Isoquercitrin in Overweight and Obese Subjects

I. Aim and Hypotheses

Specific Aim 1: To compare the body fat reducing effect of 360mg/day enzymatically modified isoquercitrin (EMIQ) with that of a placebo.

Hypothesis 1: Compared to a placebo, participants receiving EMIQ supplementation will have a greater reduction in total body fat as evidenced by measures of whole body DXA scan, skinfold thickness, waist to hip circumference ratio, resting metabolic rate, plasma adiponectin levels, physical activity, and dietary intake.

Specific Aim 2: To determine the safety of long term intake of EMIQ.

Hypothesis 2: Long-term intake of EMIQ has no ill effect on participant health as evidenced by measures of heart, liver, kidney function, and psychological state.

II. Background and Rationale

Dietary quercetin is a natural bioactive polyphenol with potential health benefits and the capacity to prevent development of various diseases including those of the cardiovascular system, central nervous system and others [1-3]. It is widely distributed in various plant foods such as onions, broccoli, concord grapes, apples and more [4]. In plants, quercetin is present as conjugated with different forms of glucosides [5], which affect their bioavailability. The bioavailability of different forms of quercetin has been the subject of several investigations [6]. Enzymatically-modified isoquercitrin (EMIQ) is a mixture of quercetin monoglucoside and its α -oligoglucosides, which mainly consist of quercetin-3-O- β -glucoside (Q3G) and α -glucosyl derivatives with 1-7 of additional linear glucose moieties [7, 8]. Supplementing the diet of apoE-deficient mice with EMIQ increased quercetin levels and suppressed atherogenesis in this mouse model of human atherosclerosis[9]. In human trials, the bioavailability of EMIQ

has been shown to be 17-fold higher than quercetin aglycone [10]. After efficient absorption of EMIQ, quercetin is released, and it exerts its biological activity such as reducing body fat, improving cardiovascular health and reducing blood pressure.

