Week 4, Visit 3: Subjects will be asked to return to the MRU 4 weeks (± 1 week) from visit 2. This visit is required to monitor volunteer health and safety during EMIQ supplementation of 360mg/day for 4 weeks. Subjects will be asked to arrive fasted for 12 h and bring their unused supplements as well their compliance calendar. Vital signs, scrub weight and changes to volunteer health, medication and eligibility status will be assessed. Blood samples will be collected for liver and kidney function. In addition, a second EKG will be performed to monitor any changes the supplement may have on heart function. The PAR will be administered. Compliance with supplement intake will be determined by counting the unused capsules remaining in blister pack and review of compliance calendars. The second 1 to 1½ month supply of EMIQ capsules will be dispensed to the subject. A continental breakfast meal will be provided to the subjects. Subjects will be mailed a \$50 check for completion of Visit 3. After visit 3 (around week 6), subjects will complete 3 dietary recalls by phone.

Week 8, Visit 4: Subjects will be asked to come to the MRU 8 weeks after visit 2 or 4 weeks (± 1 week) after their previous visit. This visit is also required to monitor and ensure safety of EMIQ supplement intake at the dose of 360 mg/day for 8 weeks. Subjects will be asked to arrive fasted for 12 h and bring their unused supplements as well their compliance calendar. Vital signs, scrub weight and changes to volunteer health, medication and eligibility status will be assessed. Blood samples will be collected to monitor liver and kidney function. The PAR will be administered. Compliance with supplement intake will be

determined by counting the unused capsules remaining in blister pack and reviewing the compliance calendar. The final 1 to 1½ month supply of EMIQ capsules will be dispensed to subjects. A continental breakfast meal will be provided to the subjects. Subjects will be mailed a \$50 check for completion of Visit 4. After visit 4 (around week 11-12), subjects will complete 3 dietary recalls by phone.

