Week 12, Visit 5: Subjects will be asked to return to the MRU approximately 12 weeks from their baseline visit or 4 weeks (\pm 1 week) from their previous visit. Subjects will be asked to arrive fasted for 12 hours and to bring back their unused supplement and compliance calendar. Vital signs, scrub weight and changes to volunteer health, medication and eligibility status will be assessed. Blood samples will be collected and archived pending tissue banking consent. Final measurements will be taken during this visit including: routine health screening analysis, lipid profile, adiponectin, insulin test, a urine dip stick, liver and kidney function (SGOT, SGPT, BUN, creatinine, and calculated GFR), skin fold thickness and waist/hip circumference. Subjects will be asked to rest for 30 min prior to measuring systolic and diastolic blood pressures and RMR analysis, which will be conducted by study staff. After RMR and BP measurements, subjects will be escorted to the BCAC for a whole body DXA scan to measure total and segmental body fats. A three factor eating questionnaire, food craving questionnaire, and the PAR will be administered to assess changes in volunteer's dietary inhibition, restraint, hunger, cravings and activity level throughout the study. Compliance with supplement intake will be determined by counting the unused capsules remaining in blister pack and by reviewing the compliance calendar. A continental breakfast meal will be provided to the subjects. Subjects will be mailed a \$305 check for completion of the final study Visit 5.

Below is an outline of the visits mentioned above:

Visit	Procedures	Length
Screening	Obtain Vital Signs Height, Scrub Weight and BMI 10mL Blood Draw* Urine Sample Review Inclusion/ Exclusion Criteria Review Health History Complete Beck Depression Inventory *Some women may be required to give an additional 3mL blood for a pregnancy test	2 Hours
Visit 1	Assess Health/Medication/Eligibility Changes Receive Instructions/Materials for Dietary Recalls	1 Hour
Between Visits 1 and 2	No visit required. Volunteers will be called 3x for 24-hour dietary recalls.	
Visit 2	Assess Health/Medication/Eligibility Changes Obtain Vital Signs Height, Scrub Weight and BMI Undergo EKG Measurement Urine Sample 30 Minutes Bed Rest Followed By RMR Measurement Hip/Waist Circumference Skinfold Thickness 17mL Blood Draw DXA Measurement Administer Questionnaires Receive Supplement/Instructions/Compliance Calendar	5 Hours

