Visit 2, Baseline: A 10mL (2 teaspoons) blood sample will be drawn into red marble top tubes for liver and kidney function tests, insulin and adiponectin. An additional 7mL (1.4 teaspoons) of blood will be drawn into lavender top tubes for analysis of lipids. A spot urine sample will be provided for urinalysis.

Visit 3, Week 4: A 5mL (1 teaspoon) blood sample will be drawn into a gold topped tube for liver/kidney function testing.

Visit 4, Week 8: A 5mL (1 teaspoon) blood sample will be drawn into a gold topped tube for liver/kidney function testing.

Visit 5, Final: A 3mL (0.6 teaspoons) blood sample will be drawn into a lavender topped tube for CBC differential analysis. A 10mL (2 teaspoons) blood sample will be drawn into red marble top tubes for liver and kidney function tests, insulin and adiponectin. An additional 7mL (1.4 teaspoons) of blood will be drawn into lavender top tubes for analysis of lipids. A spot urine sample will be provided for urinalysis.

*Note: Visits 3 and 4 will be used to monitor participant's liver and kidney function during the study. If the study physician determines that liver function appears to be in jeopardy, subjects will be asked to discontinue the supplement and to take medical action at the discretion of the study physician.

*Note: Abnormal lab values found at screening will be provided to the volunteers in writing. Abnormal values for safety labs (those falling outside of the study physician's predetermined range) will be repeated. The study physician will be notified and determine any follow-up action.

Nutritional Intake and Physical Activity:

Subjects will receive a Food Amount Booklet and information about the 24-hour recalls at visit 1. The Dietary Assessment Unit will collect three (3) 24-hour recalls by phone (two weekdays and a weekend) between visits 1 and 2. Three recalls will be collected by phone again between visits 3 and 4 (around week 6, midway through the 12 week supplementation period) and between visits 4 and 5 (around weeks 11-12). Dietary intake data will be analyzed using Nutrition Data System for Research software version 2015, developed by the Nutrition Coordinating Center (NCC), University of Minnesota, Minneapolis, MN.

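### Liver and kidney results from weeks 4 and 8, and those of subjects who do not complete, have no stated route into the between-arm safety comparison

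*SAP*

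**What the plan says.** Protocol section I makes safety Specific Aim 2. Hypothesis 2 reads "Long-term intake of EMIQ has no ill effect on participant health as evidenced by measures of heart, liver, kidney function, and psychological state".

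The draws are in Protocol III.E.I (visit descriptions) and III.E.IV (Study Assessments):
- Visit 2 (baseline): a sample "drawn into red marble top tubes for liver and kidney function tests, insulin and adiponectin".
- Visit 3 (week 4): "Blood samples will be collected for liver and kidney function".
- Visit 4 (week 8): "Blood samples will be collected to monitor liver and kidney function".
- Visit 5 (week 12): liver and kidney function again, with AST, ALT, BUN, creatinine and calculated GFR listed.

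The stated purpose of the middle two draws is individual monitoring: "Visits 3 and 4 will be used to monitor participant's liver and kidney function during the study". The study physician decides on any action.

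The SAP's Statistical Analysis Plan section is one paragraph. It includes subjects who completed the study. It uses Student's t-test for group differences, with a two-sample Wilcoxon test when distributional assumptions look doubtful. For categorical variables it gives counts with percentages and Fisher's exact or chi-square tests. Its only named time point is in this sentence: "Model assumptions were assessed within an ANCOVA model predicting 12 week outcome, adjusting for baseline". It names no safety endpoint. Protocol III.B (Sample Size and Statistical Analyses) deals only with weight and fat outcomes.

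**The concern.** Laboratory harm may appear as a large rise in a few subjects, and it may come and go between baseline and week 12 or be the reason a subject stops. An analysis centred on week-12 values in completers is poorly placed to show either pattern.

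The completer rule adds to this. Protocol III.C lists negative health effects among the withdrawal criteria, and III.E.IV has subjects stop the supplement if the study physician judges liver function to be in jeopardy. Such a subject may not complete, and the week 4 or week 8 value may then be the only laboratory evidence of harm. The trial could report no difference in liver or kidney function between arms without those values having been compared.

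**Working it through.** **The plan's own figures.** No sample size, power or threshold is given for safety. The only sizing is for abdominal fat loss. The protocol's formula with the simple mean of the two SDs, (24.62 + 12.87)/2 = 18.745, and a difference of 19 − 1 = 18 gives 1 + 16 × 18.745²/18² = 18.35, matching the stated 18 per group. It has no bearing on this point.

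**What is drawn and what is specified.** There are three post-baseline draws (weeks 4, 8, 12). The SAP names one time point, week 12, so 2 of 3 draws have no specified arm-level analysis. The protocol enrols 64 to obtain 50 completers, so it allows for 14/64 = 21.9% of enrolled subjects falling outside the analysis set.

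**Rise at week 4 only.** Assumptions, none from the documents: standardised lab value, correlation 0.6 between visits, 25 per arm, affected EMIQ subjects rise by 5 SD, abnormal means above 3 SD; 20,000 runs. With 6 of 25 affected:
- t-test on week-12 change: rejects in about 4.9% of runs, the null level;
- Fisher's exact test on abnormal at any visit: rejects in about 81%.

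With 3 of 25 affected, neither test finds it (about 5% and 0%), but a count would show it.

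**Rise at week 12.** Assumptions: ALT mean 25, SD 10, truncated at 5; 25 per arm; k EMIQ values multiplied by 5.

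| k of 25 | t-test rejects | Wilcoxon rejects | EMIQ mean ± SD | Fisher p, k vs 0 |
|---|---|---|---|---|
| 2 | 4–5% | about 6% | 33 ± 31 | 0.49 |
| 3 | about 12% | about 9% | 37 ± 37 | 0.23 |
| 5 | about 61% | about 17% | 45 ± 46 | 0.0502 |
| 6 | about 85% | about 25% | 49 ± 50 | 0.022 |

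Placebo is 25 ± 10 throughout. The EMIQ mean follows directly: for k = 2, (23 × 25 + 2 × 125)/25 = 33. Wilcoxon, the SAP's fallback when distributions look wrong, is the less sensitive of the two from k = 3 upward.

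**What a count can and cannot do at this size.** Exact 95% intervals are 1.0–26.0% for 2/25 (8%) and 2.5–31.2% for 3/25 (12%). Two-sided Fisher p for k versus 0 is 2 × C(25,k)/C(50,k). For k = 5 this is 2 × 53,130/2,118,760 = 0.0502; for k = 6 it is 2 × 177,100/15,890,700 = 0.022. At least 6 versus 0 is needed for p < 0.05. Zero cases in 25 still leaves a one-sided 95% upper bound of 1 − 0.05^(1/25) = 11.3%.

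**The case against.** Much can be said for the plan, and several stronger readings fail against it.

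- A reader might infer that the SAP compares only averages. It does not: Wilcoxon compares ranks, and the same paragraph plans counts and Fisher or chi-square tests. What is missing is a defined abnormality variable, not a method.
- A reader might infer that the week 4 and 8 results are discarded. The SAP's week-12 sentence is about checking model assumptions and names no safety lab, and the t-test sentence gives no time point. Use of the middle draws is unspecified, not excluded.
- A reader might infer that the planned summary hides individual toxicity. A week-12 rise in a completer enters the mean, and an SD of about 31 against 10 would be noticed.
- A reader might set the low rejection rates of the t-test against a count and conclude that the count is the sharper tool. That compares a test with a description. Tested like for like at week 12, Fisher's exact test cannot reach p < 0.05 below 6 versus 0 and does no better than Student's t for small numbers.
- Protocol III.G counts abnormal laboratory findings as adverse events, requires adverse event summaries to the IRB and has the data reviewed at least twice a year. Abnormal safety labs are repeated and go to the study physician.

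All of this stands. However, none of the monitoring steps is stated to compare arms, and no text brings a week 4 or week 8 value, or a non-completer's value, into the result for Aim 2.

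**Conclusion.** The concern holds as a gap in specification. In the SAP's Statistical Analysis Plan section, a laboratory change that resolves before week 12 or leads to withdrawal has no stated route into the between-arm safety result. A few large week-12 changes are diluted in the planned tests, though visible in the SD.

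The schedule, the completer rule and the absence of a defined abnormality variable are read directly from the documents. The rejection rates are illustrations that depend on the assumed distributions, correlation and size of rise. The transient case does not depend on the size of the rise, because a change absent at week 12 cannot move a week-12 comparison. The Fisher limit and exact intervals depend only on 25 per arm. The point is worth correcting because safety is one of only two aims and the data are already collected. It does not show that harm was missed.

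**What to change.** Add a short safety-laboratory section to the SAP:

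1. **Population.** Every randomised subject who took study capsules and has at least one post-baseline lab, completer or not.
2. **Worst value.** For each analyte, the worst value over all available draws at visits 3, 4 and 5, in the adverse direction: high for AST, ALT, BUN and creatinine; low for GFR and albumin. List the analytes for each visit, since the protocol does not itemise the visit 3 and 4 panels.
3. **Report by arm.** Number and percentage outside the laboratory's reference limit at any post-baseline visit, with exact 95% CIs; the risk difference with a CI by a named method; and a baseline-to-worst shift table. State which draw is baseline, because the screening description and the visit 2 blood scheme differ on this. Give the number of draws per subject by arm, since a subject with fewer draws has fewer chances to cross the limit.
4. **Status.** Present this as descriptive estimation, for the reason shown above (6 versus 0 at 25 per arm).
5. **Keep** the 12-week means as a supplement.

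The cost is a few SAP lines and some tables, with no new blood draws. The small downside is that worst-of-three values are more extreme than single values in both arms, so they must be read against placebo and not alone.
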